5.1.3.3 BMS-986258 in Combination with Nivolumab Expansion Cohorts (Part C)

The purpose of the BMS-986258 cohort expansion is to gather preliminary efficacy information in specific patient populations regarding BMS-986258 in combination with nivolumab.

In the BMS-986258 cohort expansion in combination (Part C), the preliminary efficacy of BMS-986258 in combination with nivolumab may be explored in selected populations with RCC, NSCLC, CRC, TNBC, and SCCHN. Please refer to Section 5.4.7 and Section 6 Study Population for additional details.

Treatment in Part C will be initiated when the RP2D, MTD, or MAAD for BMS-986258 in combination with nivolumab has been determined based on evaluation of the totality of available clinical safety, PK, PD, and modeling data from Parts A, A1, and B, including information from the NSCLC PD cohorts. The dose(s) selected for Part C will not exceed the MTD or MAAD

determined in Parts A and B. Part C may begin while Part B continues to

Participants with stable disease (SD), partial response (PR), or complete response (CR) at the end of a given cycle will continue to the next treatment cycle. Participants will be allowed to continue study treatment until the first occurrence of any of the following:

- Confirmed progressive disease defined by Response Evaluation Criteria in Solid Tumors (RECIST) v1.1 (Appendix 5) unless participants meet criteria for treatment beyond progression (Section 8.1.3).
- Clinical deterioration suggesting that no further benefit from treatment is likely.
- Intolerability to therapy.
- Participant meets criteria for discontinuation of study treatment as shown in Section 8.1.
- Completion of the maximum number of cycles (12 cycles).

Continuous evaluation of toxicity events in the BMS-986258 cohort expansions will be performed throughout enrollment for all expansion cohorts. If, at any time, the aggregate rate of treatment-related toxicities meeting DLT criteria exceeds across all participants treated in cohort expansions, the findings will be discussed and further enrollment will be interrupted. Depending on the nature and grade of the toxicity, and after assessing the benefit/risk ratio, a new dose for all cohorts may be initiated at a previously tested lower dose level or at a dose level to previously tested lower dose levels.

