5.1.5 Data Monitoring Committee and Other External Committees

BMS has in place a multi-layered process for ensuring patient safety through close collaboration of study site investigators, the BMS study team, and the BMS Global Pharmacovigilance and Epidemiology (GPVE)-led Medical Surveillance Team (MST). This collaborative process constitutes the Data Safety Monitoring Plan for the study as detailed below:

Study safety is evaluated continuously by representatives of BMS GPVE, who operate independently from the clinical team and monitor safety across all BMS protocols. AEs are monitored continuously by GPVE. Signal detection is performed at least monthly and ad hoc throughout the study by the MST composed, at a minimum, of the GPVE medical safety assessment physician (Chairman of the MST) and GPVE single case review physician, the study medical monitor(s), the study biostatistician, and epidemiologist. The MST monitors actual or potential issues related to patient safety that could result in a significant change in the medical benefit/risk balance associated with the use of study drugs. Furthermore, investigators will be kept updated of important safety information, such as DLTs, during teleconferences between investigators and the BMS clinical team that will be held at least every 2 weeks during dose escalation and at least monthly during cohort expansion. If appropriate, select safety issues may be escalated to a senior level, multidisciplinary, BMS-wide Medical Review Group for further evaluation and action.

To support safety oversight, BMS has established ongoing processes for collection, review, analysis, and submission of individual AE reports and their aggregate analyses. Because this is an open-label study, the BMS medical monitor and the investigators will have access to all data necessary for safety evaluation.

All participants in this study represent individuals with high unmet medical need, as the prognosis for advanced/metastatic solid tumors is generally very poor.

BMS has elected not to use a Data Monitoring Committee for this study. In addition to the comprehensive safety-monitoring plan outlined above, the following key points were considered for this decision:

• This is an open-label study.

The eligibility criteria exclude participants with disease characteristics that could predispose to higher risk of morbidity.

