5.4.7 Rationale for Tumor Selection for Expansion (Part C)

Five tumor types were chosen for the study. The following specific populations may be chosen for Part C:

- RCC participants who received and progressed on or after anti-PD-1 therapy as monotherapy or in combination with other I-O agents)
- MSI-H CRC participants who received and progressed on or after-anti-PD-1 therapy, and MSS CRC participants
- NSCLC participants who received and progressed on or after-anti-PD-1 therapy
- SCCHN participants who received and progressed on or after anti-PD-1 therapy
- Recurrent or metastatic TNBC participants

The precise indications that will be evaluated in these tumor types were defined based on current results (or lack of) with immune-oncology agents, but also on the premise that TIM-3 and PD-1 are frequently co-expressed and TIM-3 may arise as a mechanism of resistance for anti-PD-1 therapy.

Given its inherent immunogenic characteristics, RCC was among the first tumor types to be studied in the context of immunotherapy. High-dose IL-2 was approved in 1992 for the treatment of RCC and remained an important treatment option for 2 decades. More recent discoveries of molecular and immunological alterations led to the approval of nivolumab for previously treated advanced RCC, based on an ORR of 25% in comparison with 5% for everolimus. Recently published results demonstrated response rates of around 40% with the combination of nivolumab and ipilimumab for patients with metastatic RCC. Progress is being made, but despite recent advances, most patients with advanced RCC will succumb to their disease.

The current standard treatment for patients with metastatic CRC is fluorouracil-based chemotherapy regimens combined with agents targeting angiogenesis or epidermal growth factor receptor (EGFR). ⁵⁴ Based on results from the Phase 2 CheckMate-142 trial, nivolumab was

Protocol Amendment No.: 07

approved for the treatment of patients with MSI-H or mismatch repair-deficient (MMR-D) metastatic CRC⁵⁵ but MSI-H patients correspond to 5% of the patient population with metastatic CRC. MSS colon cancers, which make up the majority of the tumors, do not respond to anti-PD-1 monotherapy. TIM-3 is expressed in the immune infiltrate in CRC; therefore, BMS-986258 may be active in this indication.

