10.1.2 Cohort Expansion

The purpose of cohort expansion is to gather additional safety, tolerability, preliminary efficacy, PK, and PD information regarding BMS-986258 in combination with nivolumab. However, the sample size is strictly based on efficacy, specifically on the target ORR relative to historic response rate.

Part C will be an expansion phase for BMS-986258 in combination with nivolumab and may include participants with RCC, CRC, NSCLC, SCCHN, and TNBC. Enrolled participants with RCC, SCCHN, NSCLC and CRC MSI-H will be relapsed or refractory to prior PD-(L)1 treatment. Participants with a diagnosis of RCC, CRC, NSCLC, and SCCHN may be selected

Each disease cohort expansion will be handled independently and there will be no multiplicity adjustment. Up to participants may be treated per expansion cohort (for a total of in Part C overall) to allow for if needed per tumor cohort, although a total of up to participants need to be treated across tumor cohorts based on the sample size assumptions and characteristics in the 2-stage design shown below.

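### The only visible rate-based toxicity trigger in Part C pools all tumor cohorts; a conservative per-cohort check against the same threshold would be a cheap addition

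*Combined protocol and SAP*

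**What the plan says.** Section 5.1.3.3 has toxicity evaluated continuously, throughout enrollment, for all expansion cohorts. Its one visible rate-based trigger is that "the aggregate rate of treatment-related toxicities meeting DLT criteria exceeds across all participants treated in cohort expansions". The gap after the verb is a blacked-out threshold, called T here. If T is exceeded, "the findings will be discussed and further enrollment will be interrupted". After a benefit/risk assessment, "a new dose for all cohorts may be initiated at a previously tested lower dose level".

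Section 10.1.2, on the efficacy sample size, says: "Each disease cohort expansion will be handled independently and there will be no multiplicity adjustment". Section 5.2 refers to 5 tumor cohorts, but Section 5.4.7 leaves open which will run: "The following specific populations may be chosen for Part C".

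Other oversight carries no visible rate:
- **Section 5.1.5:** "Signal detection is performed at least monthly and ad hoc throughout the study by the MST", a team that includes the study biostatistician; investigator teleconferences "and at least monthly during cohort expansion"; and "select safety issues may be escalated to a senior level, multidisciplinary, BMS-wide Medical Review Group". There is no Data Monitoring Committee.
- **Section 3.3.6:** the sponsor and investigators may decide at any time on dose modification, further safety measures or stopping the study.
- **Sections 7.1.1 and 8.1:** drug hold and discontinuation for individual participants with DLT-criteria events.

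**The concern.** The visible trigger has a single denominator. If toxicity were concentrated in one tumor type, the other cohorts would dilute it, and the pooled rate could stay under T while that cohort was well above it. I found no cohort-level rate criterion in Sections 3.3.6, 5.1.3.3, 5.1.5, 7.1.1, 8.1, 10.1.2, 10.3.2 or 10.3.8. The Part C interim analysis in 10.3.8 rests on tumor data, not toxicity.

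Safety is the primary objective, and Section 10.1.2 lists it among the purposes of Part C. What is at stake is whether the teams that already review safety have a pre-stated guide to when one cohort's count is more than chance.

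**Working it through.** **No figure to reproduce.** T, the cohort sizes and the total are blacked out, and no operating characteristics for this trigger are visible. Everything below except the count of 5 cohorts is an assumption.

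**1. Dilution.** Let s be the affected cohort's share, q its true rate and b the rate elsewhere. The expected pooled rate is s·q + (1−s)·b. With K equal cohorts, q = 45% and b = 10%, this is (0.45 + 0.10(K−1))/K:
- K = 5: 0.85/5 = 17%
- K = 3: 0.65/3 = 22%
- K = 2: 0.55/2 = 27.5%

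The rate that the affected cohort needs for the expected pooled rate to reach T is q* = (T − (1−s)·b)/s. With s = 0.20 and b = 0.10:
- T = 20%: (0.20 − 0.08)/0.20 = 60%
- T = 25%: (0.25 − 0.08)/0.20 = 85%
- T = 30%: 110%, impossible
- T = 33%: 125%, impossible

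**2. Continuous looks soften this.** An early run of events can cross T before dilution sets in. The table gives the chance that known events divided by participants treated ever exceeds T. One cohort is at 45% and the others at 10%, with 20 to 30 per cohort and random enrollment order. Lag is the number of further enrollments before an outcome is known.

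| Setting | T=20% | T=25% | T=30% | T=33% |
|---|---|---|---|---|
| 5 cohorts, no lag, from participant 20 | 60–62% | 27% | 10–11% | 6–7% |
| 5 cohorts, lag 3, throughout | 63–66% | 32% | 17% | 14% |
| 5 cohorts, lag 5, throughout | 52–54% | 20–21% | 7% | 5% |
| 3 cohorts, lag 3 | 84–88% | 56–59% | 33–34% | 26–27% |
| 2 cohorts, lag 3 | 94–97% | 78–85% | 57–62% | 48–51% |

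**3. Sensitivity to other unknowns** (five cohorts of 20, lag 3, T = 20/25/30/33%). With a 15% background the chance is about 86/56/32/25%, part of which is background crossing. If the affected cohort enrolls first, it is about 99/97/92/88%.

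**4. A per-cohort check.** For x events in n participants under a Beta(0.5, 0.5) prior, the posterior is Beta(x+0.5, n−x+0.5). Flag the cohort if Pr(rate > T) > 0.95, from n = 6. At T = 30% this gives 4/6, 5/8, 6/10, 8/15 and 10/20. Exact results for T = 25–33% and cohorts of 20 to 30:
- detection of a 45% cohort: 49–87%
- a false flag in any of five cohorts: 0.7–2% at a true 10%, 4–11% at 15%, 11–33% at 20%

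A looser 0.85 cutoff detects 71–97%, but its any-of-five false flags are 2–15%, 9–42% and 26–74%. That is too many.

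**5. Both rules together.** A pause here means that either rule is crossed (five cohorts of 20–30, pooled looks at lag 3, cohort check without lag, 0.95 cutoff, T = 25–33%). In the 45% scenario the chance of a pause rises from about 13–32% to 53–89%. At a uniform rate in all cohorts, total pauses rise by about 1 point at 10%, 2–5 points at 15% and 6–8 points at 20%. I re-ran this step and the results agree within simulation error.

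**The case against.** The strongest reply is that pooling is a sound choice here. Part C gives one combination, the visible follow-on action covers all cohorts, and a pooled rate is less noisy than rates in small cohorts. Sections 3.2.2 and 3.3.7 describe nivolumab monotherapy safety as similar across tumor types. The one exception is pulmonary inflammation, possibly more frequent in NSCLC, and 3.3.7 ties it partly to difficulty in attributing pulmonary findings. Section 5.1.3.3 has NSCLC PD-cohort information feed the decision to start Part C. Section 3.3 reports no DLTs in 25 monotherapy participants or in 4 on the combination. Nothing in the documents suggests 45% in one tumor type against 10% elsewhere.

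Most of this stands, and it rules out three stronger readings that a reader might infer:
- **That the plan contradicts itself.** The independent handling in 10.1.2 concerns efficacy and multiplicity. It promises no cohort-level toxicity rule.
- **That no one looks at cohorts.** Evaluation covers all expansion cohorts, and the review in 3.3.6 and 5.1.5 can act without any trigger.
- **That the loss of sensitivity is large.** It cannot be sized without T, cohort sizes, background rate and enrollment order.

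What survives is narrower. The dilution follows from the visible denominator whatever T is, and none of the other safeguards shows a cohort rate criterion. The false-alarm objection defeats the 0.85 boundary but not a conservative one.

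**Conclusion.** This is a cheap improvement, not an error. The one visible numeric backstop in Part C is insensitive to an excess confined to one cohort when that cohort is a small share of the total. How much this matters is undetermined. It matters less if few cohorts open, if the affected cohort enrolls first, or if T is about 20%, and with a single open cohort it vanishes. In the assumed scenario of five interleaved cohorts with T of 25–33%, the pooled rule with a lag of three misses roughly two thirds or more of affected trials. The 45% and 10% rates, the 20 to 30 per cohort, the random order and the lag are all illustrative. The absence of a cohort rule holds only for the visible text.

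**What to change.** Keep the pooled trigger and T. At each planned safety review, also tabulate the DLT-criteria rate by tumor cohort against the same T. Use a pre-tabulated, conservative boundary with a minimum n, counting participants whose outcomes are known. The 0.95 posterior cutoff from n = 6 is one example.

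A crossing would prompt the discussion already planned in Section 5.1.3.3. The sponsor should state whether any enrollment interruption then covers that cohort or all of Part C. The sponsor chooses the cutoff, prior and minimum n, and confirms operating characteristics with realistic reporting lag and accrual; the illustration applied no lag to the cohort check. No dose or clinical rule is proposed.

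The cost is a short paragraph and one table, plus the extra pauses given above. If a cohort rule already exists in blacked-out text, nothing needs to change.

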7.1.1 Dose-Limiting Toxicities

For the purpose of guiding decisions regarding dose escalation in Parts A and B, DLTs will be defined based on the incidence, intensity, and duration of AEs for which no clear alternative cause is identified. The DLT period will start on the first day of Cycle 1 and end at Day 28 (therefore, 4 weeks) in Parts A and B. The severity of AEs will be graded according to NCI CTCAE v4.03.

[figure not shown]
Protocol Amendment No.: 07

For the purpose of participant management, DLTs that occur at any time, whether during dose escalation (Part A or B), SC dose(s) (Part A1), or cohort expansion (Part C), will result in study drug being held pending evaluation of the event being related to study drug, in accordance with Section 7.4.

A participant is considered DLT evaluable if receiving 1 dose of BMS-986258 in Part A or 1 dose of BMS-986258 and nivolumab 480 mg in Part B and completing the DLT observation period. Participants who withdraw from the study during the 4-week DLT evaluation period for reasons other than a DLT may be replaced with a new participant at the same dose level. The incidence of DLT(s) during the 4-week DLT evaluation period will be used in dose escalation decisions and to define the MTD/RP2D in monotherapy and in combination with nivolumab. AEs occurring after the 4-week DLT period will be considered for the purposes of defining the RP2D upon agreement between the Sponsor and Investigators. Participants experiencing a DLT will not be retreated with study drug and will enter the safety follow-up period of the study.

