10.2 Populations for Analyses

For purposes of analysis, the following populations are defined in Table 10.2-1 below:

Table 10.2-1: Population for Analyses

Population	Description
Enrolled	All participants who sign informed consent and are registered into the IRT.
Treated	All participants who take at least 1 dose of study treatment.
Response-evaluable	All treated participants with measurable disease at baseline and one of the following: (a) at least 1 post-baseline tumor assessment, (b) clinical progression, (c) death.
Pharmacokinetic	All treated participants who have concentration-time data.
Immunogenicity	All treated participants who have baseline and at least 1 post baseline pre-infusion immunogenicity assessment.

Abbreviations: IRT, Interactive Response Technology.

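### The Part C enrollment trigger counts participants from their first dose, so under brisk accrual the computed toxicity rate is temporarily too low and the pause comes later

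*Combined protocol and SAP*

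**What the plan says.** Protocol Section 5.1.3.3 states that evaluation of toxicity in the expansion cohorts "will be performed throughout enrollment for all expansion cohorts". The trigger begins "If, at any time, the aggregate rate of treatment-related toxicities meeting DLT criteria exceeds" a level that is blanked out in the public copy, and continues "across all participants treated in cohort expansions, the findings will be discussed and further enrollment will be interrupted". The missing figure is a redaction, not a gap in the plan.

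Table 10.2-1 (Section 10.2) defines the treated population as "All participants who take at least 1 dose of study treatment", so a participant counts from the day of first dosing.

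Section 7.1.1 treats follow-up differently for dose escalation. The observation period starts on the first day of Cycle 1 and is to "end at Day 28 (therefore, 4 weeks) in Parts A and B". A participant is DLT-evaluable after receiving the assigned dose "in Part B and completing the DLT observation period". No readable text gives Part C an observation window, a minimum follow-up, a minimum number before the first look, or a pause for follow-up.

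**The concern.** The numerator needs time to accumulate and the denominator does not. A participant dosed yesterday adds one to the denominator and, in practice, nothing yet to the numerator. The computed rate therefore depends on how fast participants are being enrolled as well as on how toxic the combination is. The error runs in one direction, and it is largest early in accrual, when a pause would spare the most people.

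This is separate from dilution between tumor cohorts, because it arises even if every cohort has the same toxicity rate. Safety of the combination is part of the primary objective (Section 4), there is no Data Monitoring Committee (Section 5.1.5), and this is the only rate-based enrollment rule readable for Part C.

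**Working it through.** The plan shows no figure to reproduce: the threshold and Part C sizes are redacted, and no operating characteristics for this rule are readable.

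**Inputs from the protocol.** Denominator: all treated, pooled (5.1.3.3), counted from one dose (Table 10.2-1). Checks: at any time (5.1.3.3). Window: 28 days, written for Parts A and B (7.1.1) and borrowed here for Part C.

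**Assumptions.** Threshold 30%; accrual of 5, 10 or 20 per month over all cohorts; onset spread evenly over Days 0–28 (even) or Days 14–28 (late).

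**Step 1: size of the dilution.** With steady accrual for T days (T at least 28), follow-up is uniform from 0 to T. The computed rate, as a fraction of the true 28-day rate, is the mean of the onset distribution function over that range.

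- Even onset: (14 + T − 28)/T = 1 − 14/T
- Late onset: (7 + T − 28)/T = 1 − 21/T

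| Time since first enrollment | T (days) | Even | Late |
|---|---|---|---|
| 1.5 months | 45.6 | 69% | 54% |
| 2 months | 60.8 | 77% | 65% |
| 3 months | 91.2 | 85% | 77% |

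**Step 2: the same effect by number treated.** With N treated, a accrued per 28 days at even spacing, even onset and true rate p, the expected computed rate is p × [N − (a + 1)/2]/N. For p = 40% and N = 20:

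- a = 4: 0.40 × 17.5/20 = 35%
- a = 8: 0.40 × 15.5/20 = 31%
- a = 12: 0.40 × 13.5/20 = 27%

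At N = 40 the values are 37.5%, 35.5% and 33.5%, so the gap closes as enrollment matures.

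**Step 3: a single look.** Suppose 20 are treated, 8 are still inside 28 days, and there are 4 events, all among the other 12. The written ratio is 4/20 = 20%. Among the 12 it is 4/12 = 33%.

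**Step 4: delay of the trigger.** Simulation with Poisson accrual, weekly checks from 10 treated and a cap of 100. The present rule is compared with a rule that also pauses when the ratio among participants first dosed at least 28 days earlier exceeds the threshold, once there are at least 10 of them. Mean number treated at the trigger, true rate 40% (ranges run from even to late onset):

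| Accrual per month | Present rule | Second ratio added |
|---|---|---|
| 5 | 17–20 | 16–17 |
| 10 | 23–31 | 21–23 |
| 20 | 41–56 | 32–35 |

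The present rule fires in about 98% or more of runs. Counting the remainder at 100 or leaving them out moves each mean by less than one.

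**Step 5: pauses at lower true rates** (range over accrual and onset settings):

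| True rate | Present rule | Second ratio, minimum 10 | Complete follow-up, same threshold |
|---|---|---|---|
| 15% | 0–8% | 10–13% | 15% |
| 20% | 1–24% | 26–34% | 36% |

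If the second ratio applies with no minimum number, pauses at a true 15% rise to 26–35%. Repeat runs of Steps 4 and 5 agree to within about 2 participants and 2 percentage points.

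**The case against.** The strongest case against has four parts.

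*The size is unknown and may be small.* This stands. The key inputs are not readable. At 5 per month the gain is one to three participants. At 10 per month with even onset the median number treated at the trigger hardly moves (about 18, against 17–18). A true rate of 40% is also demanding: the Part C dose may not exceed the MTD or MAAD, and Section 3.3 reports no DLTs in 25 monotherapy participants or in 4 combination participants.

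*A second ratio is a stricter rule in disguise.* This stands if no minimum number is set, since one event among the first one to three qualifying participants would then halt every cohort. With a minimum of 10 it does not hold: the pause rates in Step 5 stay at or below those of the same threshold with complete follow-up. The cost is still real, and it grows as the true rate nears the threshold. At a true 25%, pauses rise from about 8–52% to 52–61%, against about 63% with complete follow-up.

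*The contrast with Parts A and B can be overdrawn.* This stands. A reader might infer that Part C dropped a required 28-day condition. Section 7.1.1 writes that window for escalation decisions in Parts A and B, and Sections 5.1.3.1 and 5.1.3.2 let the next dose level open before a third participant finishes it if the model's recommendation would not change. Nor do the documents say that all five cohorts enroll together or that accrual is fastest in Part C. Section 5.4.7 says the populations may be chosen, and Section 10.3.8 plans a two-stage design with an interim analysis.

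*Other safeguards exist.* Study drug is held for DLTs at any time (7.1.1), adverse events are monitored continuously by a group independent of the clinical team, and signal detection and teleconferences occur at least monthly (5.1.5). These reduce the consequence, but none is described as correcting the rate or pausing enrollment on it.

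**Conclusion.** The point holds as a temporary dilution and delay. The denominator, the entry of newly dosed participants and the downward direction all follow from the text. A reader might go further and infer that the rule hides an excess of toxicity. The documents do not support that: the deficit shrinks as follow-up matures, and the rule still fires in nearly all simulated trials at a true rate of 40%.

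The size depends on accrual. It is negligible when slow, and amounts to roughly 9 to 21 participants at 20 per month (41 − 32 and 56 − 35). These figures rest on the assumed 30% threshold, true rate of 40%, 28-day onset window and cap of 100. Section 5.1.3.3 does not limit counted events to 28 days, and the model leaves out events after Day 28. It is worth correcting because the remedy is cheap and makes the trigger much less dependent on enrollment speed.

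**What to change.** In Section 5.1.3.3, keep the present ratio and the existing threshold, and add a second ratio: DLT-criteria toxicities among expansion participants first dosed at least 28 days earlier, whether or not they are still on treatment, divided by the number in that same group. Apply it only once a stated minimum number of such participants exists. The figures above use 10; the sponsor should choose and state the number. Interrupt enrollment if either ratio exceeds the threshold, and show both at the teleconferences held at least monthly during expansion. Say also whether events after Day 28 count, so that both ratios use the same numerator rule.

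Because the present ratio stays, the combined rule can never fire later than the current one. It costs a few sentences and one more line in the safety listing, with no new data or participants. The added pauses at acceptable true rates (Step 5) should be disclosed, preferably recalculated with the actual threshold and expected accrual.
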